#### 4.1.2 Demographics

- Age (years)
  - o minimum, maximum, median, arithmetic mean
  - o Age groups and their frequencies

- Height (cm)
  - o minimum, maximum, median, arithmetic mean
- Weight (kg)
  - o minimum, maximum, median, arithmetic mean
- Gender
  - o Frequencies
- Pregnancy
  - o frequencies

## 4.1.3 Main Diagnosis

- Reason for Surgery
  - o Code with MedDRA
  - o Frequencies of coded terms

#### 4.1.4 Concomitant Diseases

- Concomitant Diseases
  - Yes / No: Frequencies
  - Frequencies of disease groups
  - Other diseases: Code with MedDRA

#### 4.1.5 Evaluation of Risk of Bleeding

- Patients with blood-thinning medication
  - o Yes / No: Frequencies
  - o Frequencies of medications
  - o Other medication: grouping of terms, if possible
- Additional coagulation disorders
  - o Yes / No: Frequencies
  - o Frequencies of disorders
  - o Other disorders: grouping of terms, if possible

#### 4.1.6 Coagulation

- Thromboplastin value
  - o Type (INR, Quick, no value): Frequencies
  - o INR: minimum, maximum, median, arithmetic mean
  - o Quick (%): minimum, maximum, median, arithmetic mean
- Partial thromboplastin time (seconds)
  - o minimum, maximum, median, arithmetic mean
- Platelet count  $(10^3/\text{mm}^3)$ 
  - o minimum, maximum, median, arithmetic mean
- Platelet activity: Normal, reduced: Frequencies

## 4.1.7 Pre- & intraoperative Measures

- Pre- & intraoperative Measures:
  - o Yes / No: Frequencies
  - o Details: Frequencies, minimum, maximum, median, arithmetic mean

- o Coagulation factor: Name, Dose, Unit
  - Frequencies, minimum, maximum, median, arithmetic
    mean
- o Other: Coding of free text, if possible

## 4.1.8 Documentation of Surgery

- Date of Surgery
- Type of Operation: Frequencies
- Minimal invasive technique: Frequencies
  - o Other: Coding of free text, if possible
- Duration of surgery (minutes)
  - o Minimum, maximum, median, arithmetic mean
- Conversion: yes / no: Frequencies
  - o Reason(s): Frequencies
  - o Other: Coding of free text, if possible
- Adverse Event: yes / no: Frequencies
- Main reason for prerolled TachoSil use: Frequencies
  - o Other reason: Coding of free text, if possible
- Hemostatic actions before TachoSil: Frequencies
  - o Details: Frequencies
  - o Other: Coding of free text, if possible
- Application of TachoSil: Frequencies
  - o Other: Coding of free text, if possible
- TachoSil replacing other therapy: Yes / No: Frequencies
  - o Details: Frequencies
  - o Other: Coding of free text, if possible
- Reason for Preference of TachoSil
  - o Details: Frequencies
  - o Other: Coding of free text, if possible
- Other advantages of TachoSil: Yes / No: Frequencies
  - o Details: Frequencies
  - o Other: Coding of free text, if possible
- Remodeling of TachoSil
  - o Details: Frequencies
  - o Other: Coding of free text, if possible
- Duration of TachoSil pressing: Frequencies
- Number of used TachoSil
  - o Minimum, maximum, median, arithmetic mean
- Location of TachoSil application
  - o Details: Frequencies
  - o Other: Coding of free text, if possible

#### 4.1.9 Assessment

- Assessment of manageability of TachoSil (1-5)
  - o Frequencies
  - o Median / Mean

- Assessment of satisfaction with TachoSil (1-5)
  - o Frequencies
  - o Median / Mean

•

#### 4.2 Final Documentation

• Date of discharge

## 4.2.1 Complications

- Any complications after TachoSil application
  - o Yes / No: Frequencies
- Number of Adverse Events
  - o Minimum, maximum, median, arithmetic mean

## 4.2.2 Evaluation

- Previous TachoSil experience
  - o Frequencies
- Surgery -specific TachoSil experience
  - o Frequencies
- Assessment of satisfaction with TachoSil (1-5)
  - o Frequencies
  - o Median / Mean
- Reason for divergent satisfaction compared to Baseline evaluation
  - o Free Text, grouping if possible
- Advantage of TachoSil
  - o Reduction of surgery time (minutes)
    - Yes / No: Frequencies
    - Difference of duration of TachoSil, compared to alternative application: Maximum, median, arithmetic mean
  - o Reduction of ICU time (days)
    - Yes / No: Frequencies
    - Difference of duration of TachoSil, compared to alternative application: Maximum, median, arithmetic mean
  - o Reduction of total care time (days)
    - Yes / No: Frequencies
    - Difference of duration of TachoSil, compared to alternative application: Maximum, median, arithmetic mean
  - o Other
    - Yes / No: Frequencies
    - Free text, grouping if possible

## 4.2.3 Discharge

- ICU stay: Yes / No: Frequencies
  - o Discharge date (ICU)
- Discharge date (hospital)

#### 4.3 Documentation of Adverse Events

Adverse Events will be reported immediately to the Sponsor's Pharmacovigilance department.

- Pregnancy: Yes No: Frequencies
- Description of Adverse Event
  - o Coding with MedDRA
    - Grouping by SOC, PT: Frequencies
- Causality: Yes / No: Frequencies
- Severity: Frequencies
- Actions taken
  - o Frequencies
  - o Other: coding if possible
- Outcome: Frequencies
  - o If sequalae: coding of free text
  - o If death: autopsy: yes no: frequencies
- Serious: Yes / No: Frequencies
- SAE criteria: checked: Frequencies

# 5 Analysis Sets

# 5.1 Safety Analysis Set

Data of all patients that are eligible, have signed the Informed Consent and have documented all mandatory forms will be analysed.

The Safety Analysis Set contains all data including demographics, surgery data, evaluation of satisfaction of TachoSil, and Adverse Events.

There is no separate Per Protocol Analysis.

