#### Statistical methods

For the analysis of data the safety population (SAF) only will be considered. The safety population consists of all patients,

- who received a patient information and who had consented to the collection, transmission and evaluation of their data (Comment: this has to be documented in the CRF and it is assumed that the consent forms are available for all patients in the corresponding study center.), and
- who underwent laparoscopic surgery in the field of gynecology, urology and visceral surgery with pre-rolled TachoSil® applied during surgery as documented in the CRF.

The SAF is used for summaries of demographic and baseline characteristics, all safety related variables and all summaries of effectiveness data. No per-protocol- set analysis will be done.

All data collected will be analyzed descriptively. In general, numerical continuous or 'quasi'-continuous data will be summarized with standard descriptive statistics including number of patients with valid data, arithmetic mean, standard deviation, minimum, median and maximum. For categorical variables tables of frequencies (absolute and relative frequencies) will be presented. The percentages are based on the number of patients in column heading unless otherwise stated. The number of patients with missing values is included in the calculation of the percentages.

Statistical analyses will be performed using validated statistical software (e.g. SAS®, SAS Institute Inc.). All statistical details including calculated variables and proposed format and content of tables will be detailed in a separate document, the statistical analysis plan (SAP). The SAP will be provided by the CRO and finalized before study database lock.

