# 7.3 Selection of Study Population

It is planned to include up to 105 Austrian and 360 German inpatients who have undergone laparoscopic surgery in the field of gynecology, urology and visceral surgery where prerolled TachoSil® was applied and who are 18 years or older.

Contraindications, such as hypersensitivity to the active pharmaceutical ingredient or to another ingredient of pre-rolled TachoSil®, are to be observed according to the current SmPC.

The observational period for individual patient will last from surgery (V0: Baseline) until date of discharge from hospital (V1: Final visit).

Data will be collected from patient files as well as study specific questions answered by the treating physician.

Written informed consent to use of collected data must always be obtained before collection of any study specific personal, sensitive data.

Subjects should be included in the study only once.

Data erroneously collected from subjects for which written consent is not available, will not be included in or will be deleted from the database.

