### **10.4 Data Management**

The CRO is responsible for Data Management carried out according to a Data Management Plan. A data management plan, which will include the description of plausibility checks, will be prepared before the start of data entry.

If the written informed consent of a patient is known not to be available in spite of it being required, data for this patient is not entered into or is deleted from the database.

If a patient is erroneously included in the study more than once only the data relating to the first inclusion will be kept in the database and be available for analysis.

If a patient is included in the study in spite of being treated off-label (not according to the SmPC), data is kept in the database and analysed as described in the Statistical Analysis Plan.

The current Standard Coding Instructions for coding of medical history, concomitant illness (MedDRA), concomitant medication (WHO-Drug) and adverse events (MedDRA) must be followed.

The patients will be identified in the database only by Study ID, Site ID, patient number, year of birth, and gender.

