### 10.4.1 Data Collection Tools and Flow

The Study Site will receive data collection tools (Case Report Forms (CRFs)) from CCI.

Whenever possible, complete data sets should be entered. Text field entries and any data collected on paper should be legible and follow the requested language standard.

The Study Site Responsible must sign off the complete data set for each patient, confirming the collected data. SAE data collected and reported according to section 9.3 should be signed off separately by a physician who may or may not be involved in the study.

The Study Site will provide completed CRFs directly to the responsible CRO syneed medidata.

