### 10.4.2 Query management

In case of incomplete or inconsistent entries regarding predefined CRF-items (e.g. informed consent, study treatment) the CRO will contact the respective physician in writing for clarification or completion of missing data.

In case of incomplete or inconsistent entries regarding AEs or SAEs, the Sponsor will contact the respective physician for clarification. Prior to database lock, a reconciliation of study-related safety information with the sponsor's safety database will be performed.

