# 11.1 Statistical Analysis Plan

This study is observational and epidemiological methods will be employed for data analyses. All statistical details including calculated variables and proposed format and content of tables will be detailed in the SAP, a separate document provided by the CRO

The SAP will be finalized before study database lock. The analysis will be performed in accordance with the European Network of Centres for Pharmacoepidemiology and Pharmacovigilance (ENCePP) Guide on Methodological Standards in Pharmacoepidemiology [R5].

Statistical analyses will be performed using validated statistical software (e.g. SAS®, SAS Institute Inc.).

Descriptive analysis will be performed of all collected data except data collected only for the purpose of data cleaning. All AEs will be listed as described in the SAP in section 5.

The main outcomes of the study are:

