## 4.1 Baseline

## 4.1.1 Informed Consent, Inclusion/Exclusion Criteria

 A valid Informed Consent, dated before start of documentation, must be present. All Inclusion Criteria must be fulfilled (and none of the Exclusion Criteria), otherwise the patient must be excluded from analysis.

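### SAP 5.1 makes completion of all mandatory forms a condition of entry to its only analysis set, labelled Safety; the safety population in the supplied 2015 protocol has no such condition

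*SAP*

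**What the plan says.** **Analysis set in the SAP.** Section 5.1 reads: "Data of all patients that are eligible, have signed the Informed Consent and have documented all mandatory forms will be analysed". This is the only set; there is no per-protocol analysis. Section 4.1.1 adds: "All Inclusion Criteria must be fulfilled (and none of the Exclusion Criteria), otherwise the patient must be excluded from analysis".

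**Analysis set in the protocol (dated 20 August 2015).** Section 2, Statistical methods, admits a patient to the SAF on two conditions: information and consent, and laparoscopic surgery in gynecology, urology or visceral surgery with pre-rolled TachoSil applied as documented in the CRF. Its use is broad: "The SAF is used for summaries of demographic and baseline characteristics, all safety related variables and all summaries of effectiveness data".

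**Incomplete data in the protocol.** Section 10.4.1 asks for completeness as an aim: "Whenever possible, complete data sets should be entered". For incomplete entries in predefined CRF items, section 10.4.2 says that "the CRO will contact the respective physician in writing for clarification or completion of missing data". The removals it names are missing consent (section 7.3: "Data erroneously collected from subjects for which written consent is not available, will not be included in or will be deleted from the database") and repeat inclusion (section 10.4: "only the data relating to the first inclusion will be kept in the database and be available for analysis"). Section 10.4 keeps off-label patients in the database and leaves their analysis to the SAP.

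**Missing values.** The protocol's Statistical methods count patients with missing values when percentages are calculated. SAP 8.2 says that missing data are not replaced, naming last observation carried forward as an example, and so form no part of the analysis.

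**The concern.** A safety set is normally defined by exposure. Here membership also depends on paperwork. If the final documentation (SAP 4.2) is a mandatory form, a patient without it also loses the AE entry and the two ratings recorded at surgery (SAP 4.1.8 and 4.1.9). Neither supplied document lists the mandatory forms; SAP section 6 mentions only mandatory fields. From these two documents the rule therefore cannot be applied reproducibly.

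The study is purely descriptive, so its results are largely settled by who is counted and over what denominator. No second set and no planned listing of excluded patients would show what the conditions remove. The AE rates and the primary Likert frequencies both come from this one set.

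**Working it through.** **1. Conditions side by side.**

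| Condition | Protocol SAF | SAP 5.1 and 4.1.1 |
|---|---|---|
| Consent | yes | yes |
| Laparoscopic surgery in a named field, product applied | yes, as documented in the CRF | yes, through the inclusion criteria |
| Age, inpatient status, other trial, contraindication | not a condition | patient excluded on any breach |
| All mandatory forms | not a condition | patient excluded if one is missing |

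The last row has no counterpart or delegation in the supplied protocol. The row above it is partly delegated: protocol 10.4 lets the SAP decide on off-label patients, and 4.1.1 does exclude those with a contraindication. Off-label use that breaches no listed criterion is not addressed.

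**2. Effect on AE rates.** The documents give no AE, exclusion or missing-data rates, so the inputs below are assumptions. The exception is N = 120 (SAP 2.1), taken here as the SAF size. Let f be the share of the SAF dropped, r the AE rate in patients kept (the rate the SAP reports), and x·r the rate in those dropped.

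SAF rate = (1 − f)·r + f·x·r = r·[1 + f·(x − 1)], so the relative difference (SAF − SAP)/SAP is f·(x − 1), whatever r is.

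| Dropped of 120 (f) | x = 0 | x = 1 | x = 2 | x = 3 |
|---|---|---|---|---|
| 3 (2.5%) | −2.5% | 0 | +2.5% | +5% |
| 6 (5%) | −5% | 0 | +5% | +10% |
| 12 (10%) | −10% | 0 | +10% | +20% |

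Twelve is one patient per planned centre (SAP 1.6). Check of the last cell: 9/108 = 8.3% in the SAP set and 3/12 = 25% in those dropped (x = 3) give 12/120 = 10.0% in the SAF; 10.0/8.33 = 1.20. In points, with r = 10% and f = 10%: x = 0 gives 0.9 × 10% = 9.0% (−1.0 point), and x = 3 gives 0.9 × 10% + 0.1 × 30% = 12.0% (+2.0 points).

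**3. Effect of the denominator rule (categorical variables only).** The SAP's example table in 7.1.1 reproduces: 213/388 = 54.90% and 175/388 = 45.10%, total 388. It has no row for missing values, which fits their removal but does not prove it.

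On the reading that missing values are removed, with a fraction m missing, protocol percentage = p·(1 − m) and SAP percentage = p. The SAP figure is therefore the protocol figure divided by (1 − m). For illustration, p is the 82%/18% split that protocol 11.3 reports for an older and different handling score; m is assumed.

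| Missing of 120 (m) | Protocol rule | SAP 8.2 as read here | Ratio |
|---|---|---|---|
| 6 (5%) | 77.9% / 17.1% | 82% / 18% | 1.053 |
| 12 (10%) | 73.8% / 16.2% | 82% / 18% | 1.111 |
| 18 (15%) | 69.7% / 15.3% | 82% / 18% | 1.176 |

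Continuous variables are not in conflict: the protocol also summarises them on patients with valid data.

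**The case against.** **A later protocol governs.** The SAP cites a protocol of 22 February 2016 that is not supplied. Its plan also differs visibly from the 2015 text: about 120 patients in Austrian centres, and no hypothesis test. The SAF may have been rewritten. This stands as a limit on every comparison here. A reader might infer that the SAP breaks its own governing protocol; the documents show a difference only from the 2015 version. The SAP also cites a data management plan of 18 February 2016, not supplied, which may define the mandatory forms.

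**The protocol's call to analyse all data.** Section 11.1 says: "Descriptive analysis will be performed of all collected data except data collected only for the purpose of data cleaning". A reader might take this as a promise to analyse every patient. With its single exception it is more naturally about data items; the patient set is fixed by the SAF definition, and the point rests on that.

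**SAP 8.2 is about imputation.** It mentions neither percentages nor denominators. A flat contradiction with the protocol is therefore not shown, only a conflict on the more natural reading.

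**Eligibility is delegated.** This is partly right, as shown above. Criteria are also checked and consent signed after surgery, so many ineligible patients may never be documented.

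**Little is lost.** A reader might infer that adverse events would be hidden or that the rates are biased downward. Neither is supported. Protocol 11.1 has AEs from the study and safety databases listed or tabulated in the final report, and the direction of bias is unknown. Mandatory-field checks and queries should also limit incompleteness. What remains is that the rates are computed in a set conditioned on form completion.

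**Conclusion.** The point holds against the supplied protocol and should be fixed; confidence is medium because the 2016 protocol is unseen. The firm part is the mandatory-forms condition: it is a stated rule, it is absent from the protocol's SAF, and the protocol's answer to incomplete entries is a query, not removal of the patient. SAP 5.1 does not present it as a change, although protocol section 11 expects changes in method to be documented in the SAP.

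The likely effect on AE rates is modest and can go either way: about −1 to +2 percentage points, assuming a 10% AE rate in patients kept, 10% dropped, and 0 to 3 times that rate in those dropped. The eligibility exclusion is a lesser point because part of it falls within the SAP's remit. The denominator point is secondary and conditional on the reading of 8.2. On that reading it scales every categorical percentage, including the primary Likert frequencies, by 1/(1 − m).

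**What to change.** 1. Check the protocol of 22 February 2016. If it changed the SAF or the denominator, cite it and document the change in the SAP.
2. Otherwise set SAP 5.1 to the protocol's SAF, delete the mandatory-forms condition and use each patient's available data.
3. Align 4.1.1 so that a patient is excluded only for failing an SAF condition, with repeat inclusions handled as in protocol 10.4. The one exception is off-label patients, including those with a contraindication: the SAP should say explicitly how they are analysed, as protocol 10.4 leaves to it.
4. List patients with incomplete forms or eligibility deviations, together with any AE.
5. In categorical tables, show a row for missing values, with percentages of all SAF patients. For the Likert items the percentage among patients with data may be added.

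The cost is wording in SAP 5.1, 4.1.1 and 8.2, one listing, and one extra row per categorical table. No new data are needed.

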# 6 Data Entry

Each participating site documents data directly in the eCRFs. Data is checked for completeness and correctness (e.g. mandatory fields, correct data type).

Users can unlock each CRF to correct wrongly entered data.

# 7 Analysis Details

Data analysis will be done using Statistics Software (Excel 2010, MedCalc 17.8.6).

Descriptive Statistics will be used (No testing of hypotheses):

- Number of observations
  - o Absolute
  - o Relative
- Arithmetic Mean
- Median
- Minimum
- Maximum

#### 7.1 Presentation of Results

Data and results will be displayed in tables and graphs.

#### 7.1.1 Tables

Tables include a table header, data rows, and a footer (containing the sums of each column).

## Example table:

Gender	n	%
male	213	54.90%
female	175	45.10%
TOTAL	388	100.00%

[figure not shown]
## 7.1.2 Graphs

[figure not shown]
The appropriate graph type will be selected and displayed:

- Pie Chart
- Column Chart
- Line Chart

X and y axis will be labelled accordingly.

## Example graphs:

# 8 Coding and Data Handling

## 8.1 Coding

Medical Coding will be used for the following categories:

- Adverse Events (MedDRA)
- ..

# 8.2 Data Handling

Missing data will not be replaced (e.g. Last Observation Carried Forward (LOCF)), thus are not part of the analysis.

## 9 Documents

Reports will be generated as PDFs in print quality. Raw Data will be available as Excel File(s).

## 11 Abbreviations

(e) CRF (electronic) Case Report Form

FPFV First Patient First Visit

ICU Intensive Care Unit

LOCF Last Observation Carried Forward

LPLV Last Patient Last Visit

MedDRA Medical Dictionary for Regulatory Activities

NIS Non-interventional Study SAP Statistical Analysis Plan

Company Confidential Information

SMPC Summary of Product Characteristics
